9.2.2 Continuous Endpoints

MMRM will be the primary approach for the analysis of continuous variables with more than one post Baseline assessment. MMRM analysis will be conducted using mixed-effect model including observed measurements at all visits. For the MMRM analysis, data collected on or after the date of ICE2 will be excluded. The mixed model includes the categorical fixed effects of visit, Baseline corticosteroid use (yes vs no), Baseline Mayo endoscopic sub-score (2 vs 3), prior TIM therapy failure (Yes vs No) and the continuous fixed covariate of Baseline measurement, if applicable. An unstructured variance covariance matrix will be used. If there is a convergence issue, an autoregressive (1) or compound symmetric (CS) covariance structure matrix will be used. The parameter estimations are based on the assumptions of data being missing at random and using the method of restricted maximum likelihood (REML).

Additional approaches, such as Return-to-Baseline Multiple Imputation (RTB-MI), in which data collected on or after the date of ICE2 will be imputed by Baseline values generated from MI model may be conducted for selected continuous endpoints.

9.2.3 Time to Event Endpoints

For the time-to-event endpoint, i.e., time to clinical response per Partial Adapted Mayo score, no missing date will be imputed and subjects will be censored at the last available assessment time.

9.3 Primary Efficacy Endpoint(s) and Analyses

9.3.1 Primary Efficacy Endpoint(s)

The primary endpoint is the achievement of endoscopic improvement (Mayo ESS of 0 or 1) at Week 8.

9.3.2 Main Analysis of Primary Efficacy Endpoint(s)

Analysis of the primary efficacy endpoint will be conducted on the ITT Population. Comparison of the primary efficacy endpoint will be performed between the ABBV-668 treatment group and historical placebo group using Bayesian approach with prior distribution **CCI** obtained from meta-analysis for the historical placebo data, and non-informative prior *Beta* (0.5, 0.5) for the ABBV-668 treatment group. The posterior probability of rate difference > 0 given data will be calculated. The mean difference and the corresponding 95% credible interval will be provided. Point estimate and 95% CI using normal approximation will be provided for the response rate for the ABBV-668 group. Plots of prior and posterior distribution for the rate difference between ABBV-668 and historical placebo will also be provided.

The attributes of the estimand corresponding to the primary efficacy endpoint are summarized in Table 1.

Table 1. Summary of the Estimand Attributes Corresponding to the Primary Efficacy Endpoint

Estimand Label	Attributes of the Estimand					Statistical Summary
	Treatment	Endpoint	Population	Handling of Intercurrent Events		
Primary: Achievement of endoscopic improvement at Week 8 vs. Historical Placebo	ABBV-668	Achievement of endoscopic improvement at Week 8	Adult subjects with moderately to severely active UC	ICE1: Premature discontinuation of study treatment (treatment policy) ICE2: Initiation or dose escalation of UC-related corticosteroids or initiation of any TIM therapy (composite) All data will be used regardless of ICE1 occurrence. Subjects will be considered as non-responders on or after the date of ICE2.	ICE1: Premature discontinuation of study treatment (treatment policy) ICE2: Initiation or dose escalation of UC-related corticosteroids or initiation of any TIM therapy (composite) All data will be used regardless of ICE1 occurrence. Subjects will be considered as non-responders on or after the date of ICE2.	Difference in proportion of subjects achieving response

9.3.3 Sensitivity and Supplementary Analyses of the Primary Efficacy Endpoint(s)

The same Bayesian approach will be also conducted based on other analyses approaches as described in Section 9.2 as sensitivity analyses.

9.4 Secondary Efficacy Endpoints and Analyses

9.4.1 Secondary Efficacy Endpoints

- Achievement of clinical remission per Adapted Mayo score at Week 8.
- Achievement of clinical response per Adapted Mayo score at Week 8.
- Achievement of clinical response per Partial Adapted Mayo score at Week 8.
- Achievement of endoscopic remission at Week 8.

9.4.2 Analyses of Secondary Efficacy Endpoints

Point estimate and 95% CI using normal approximation will be provided for the response rate for ABBV-668 treatment group. The same Bayesian approach specified in Section 9.3.2 will be also conducted based on the ITT Population, if applicable.

The attributes of the estimands corresponding to the secondary efficacy endpoints are summarized in Table 2.

Table 2. Summary of the Estimand Attributes Corresponding to the Secondary Efficacy Endpoints

Estimand Label	Attributes of the Estimand					Statistical Summary
	Treatment	Endpoint	Population	Handling of Intercurrent Events		
Binary Secondary Variable	ABBV-668 vs. Historical Placebo	Achievement of each binary secondary endpoint respectively	Adult subjects with moderately to severely active UC	ICE1: Premature discontinuation of study treatment (treatment policy) ICE2: Initiation or dose escalation of UC-related corticosteroids or initiation of any TIM therapy for UC (composite) All data will be used regardless of ICE1 occurrence. Subjects will be considered as non-responders on or after the date of ICE2.		Difference in proportion of subjects achieving response

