2.4 Sample Size Determination

The planned sample size is approximately 40 subjects.

A meta-analysis for historical placebo data from UC studies for tofacitinib (OCTAVE1/2), upadacitinib (Phase 2b and Phase 3; data on file), and ustekinumab (UNIFI) gives CCI improvement rate at Week 8. A prior placebo distribution that matches this overall rate and has a variance close to the variance of the rate estimate from CCI. The prior distribution for the ABBV-668 treatment group is set to Jeffreys non-informative prior *Beta* (0.5, 0.5). Assuming a response rate increase of 30% in the ABBV-668 group compared to historical placebo, a sample size of 40 subjects will provide more than 90% probability to demonstrate that the posterior probability of rate difference (ABBV-668 vs. external

placebo) > 0 is larger than 90%. The external placebo response may be updated if new placebo data from similar trials become available before the Primary Analysis database lock.

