3.0 Endpoints

Definitions of Efficacy Endpoints

Clinical Remission per Adapted Mayo Score: stool frequency subscore (SFS) ≤ 1 , and not greater than Baseline, rectal bleeding subscore (RBS) = 0, and endoscopic subscore (ESS) ≤ 1

Clinical Response per Adapted Mayo Score: decrease from Baseline ≥ 2 points and $\geq 30\%$, PLUS a decrease in RBS ≥ 1 or an absolute RBS ≤ 1

Clinical Response per Partial Adapted Mayo Score: decrease from Baseline ≥ 1 points and $\geq 30\%$, PLUS a decrease in RBS ≥ 1 or an absolute RBS ≤ 1

Clinical Remission per Full Mayo Score: Full Mayo score ≤ 2 with no subscore > 1

Clinical Response per Full Mayo Score: decrease from Baseline ≥ 3 points and $\geq 30\%$, PLUS a decrease in RBS ≥ 1 or an absolute RBS ≤ 1

Endoscopic Improvement: Mayo endoscopic subscore (ESS) of 0 or 1. Note that evidence of friability during endoscopy in subjects with a Mayo ESS of 0 or 1 will confer an endoscopic subscore of 2.

Endoscopic Remission: Mayo ESS = 0

Histologic remission: Geboes score of < 2.0

Histologic-endoscopic mucosal improvement: Mayo ESS ≤ 1 and Geboes score ≤ 3.1

Mucosal Healing: endoscopic (Mayo ESS = 0) and histologic remission (Geboes score of < 2.0).

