3.3 Additional Efficacy Endpoints

In addition, the primary and secondary efficacy endpoints will be analyzed at all other scheduled visits during which the assessments are measured. The following endpoints will also be evaluated at scheduled visits during which the assessments are measured, unless otherwise specified:

- Achievement of clinical response per Full Mayo score over time in subjects with a Full Mayo score of 6 to 12 at Baseline.
- Achievement of clinical remission per Full Mayo score over time in subjects with a Full Mayo score of 6 to 12 at Baseline (at visits with endoscopy).
- Achievement of SFS = 0, RBS = 0, and ESS = 0 over time (at visits with endoscopy).
- Achievement of SFS = 0, RBS = 0, and ESS \leq 1 over time (at visits with endoscopy).
- Time to clinical response per Partial Adapted Mayo.
- Achievement of SFS \leq 1 over time.
- Achievement of RBS = 0 over time.
- Change from Baseline in RBS over time.

- Change from Baseline in SFS over time
- Achievement of histologic-endoscopic mucosal improvement over time (at visits with endoscopy).
- Achievement of histologic remission over time (at visits with endoscopy).
- Achievement of mucosal healing (endoscopic and histologic remission) over time (at visits with endoscopy).
- Change from Baseline in number of extraintestinal manifestations (EIM) over time (as captured in the EIM electronic case report form [eCRF]).
- Change from Baseline in fecal calprotectin (FCP) over time.
- Achievement of FCP below 150 mg/kg over time.
- Achievement of FCP below 250 mg/kg over time.
- Change from Baseline in high sensitivity C-reactive protein (hs-CRP) over time.
- Achievement of no nocturnal bowel movements at Week 8 as assessed by the UC symptom daily diary.
Achievement of no nocturnal bowel movements at Week 16 as assessed by the UC symptom daily diary.
- Achievement of no tenesmus at Week 8 as assessed by the UC symptom daily diary.
Achievement of no tenesmus at Week 16 as assessed by the UC symptom daily diary.
- Change from Baseline in number of fecal incontinence episodes per week at Week 8 as assessed by the UC symptom daily diary.
Change from Baseline in number of fecal incontinence episodes per week at Week 16 as assessed by the UC symptom daily diary.
- Change from Baseline in number of days over a week with sleep interrupted due to UC symptoms at Week 8 as assessed by the UC symptom daily diary.

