4.0 Analysis Populations

The following populations will be used for the analyses.

The ITT Population consists of all subjects who received at least 1 dose of study drug.

The ITT Population will be used for all efficacy and Baseline analyses.

The Safety Population consists of all subjects who received at least 1 dose of study drug.

The Safety Population will be used for all safety analyses.

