9.5 Additional Efficacy Endpoints and Analyses

Additional efficacy endpoints described in Section 3.3 will be summarized at scheduled timepoints.

For additional binary endpoints, point estimate and 95% CI using normal approximation will be provided for the response rate of the ABBV-668 group. For additional continuous endpoints, the LS-mean and 95% CI will be reported for the ABBV-668 group using MMRM model, which includes visit, Baseline corticosteroid use (yes vs. no), Baseline

Mayo endoscopic sub-score (2 vs 3), TIM (including biologic and non-biologic) failure (Yes vs No) and Baseline measurement, if applicable. For endpoints with a single post-baseline visit, analysis of covariance (ANCOVA) will be used. Same covariates except for visit will be used. Similar analysis using RTB-MI may be performed as sensitivity analysis.

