Appendix D. Details for Historical Data

CCI

[figure not shown]

Table D-1 External Placebo Data for Secondary Endpoints at Week 8

Endpoints	External Data				External Rate	Prior Distribution
	OCTAVE-1	OCTAVE-2	M14-234	M14-675		
Clinical Remission per Adapted Mayo Score	NA	NA	7/154	7/174	4%	Beta (14.0, 312.4)
Clinical Response per Adapted Mayo Score	NA	NA	42/154	44/174	26%	Beta (85.7, 241.0)
Clinical Response per Partial Adapted Mayo Score	NA	NA	64/154	51/174	35%	Beta (20.9, 38.4)
Endoscopic Remission	2/122	2/112	2/154	3/174	2%	Beta (9.0, 547.8)

NA = data is not available

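### With about 40 subjects, the normal-approximation 95% CI fails for the rare remission endpoints: coverage is about 48% (endoscopic) and 82% (clinical) at the placebo rates, and 0/40 gives [0, 0]

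*SAP*

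**What the plan says.** The method appears three times in the SAP.

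- Section 9.3.2, primary endpoint: "Point estimate and 95% CI using normal approximation will be provided for the response rate for the ABBV-668 group".
- Section 9.4.2, all four secondary endpoints: "Point estimate and 95% CI using normal approximation will be provided for the response rate for ABBV-668 treatment group". The Bayesian comparison of 9.3.2 is added where applicable.
- Section 9.5: "For additional binary endpoints, point estimate and 95% CI using normal approximation will be provided for the response rate of the ABBV-668 group". No Bayesian comparison is stated there.

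On size, section 2.4 says "The planned sample size is approximately 40 subjects". On the denominator, section 4.0 says "The ITT Population consists of all subjects who received at least 1 dose of study drug". Under non-responder imputation (9.2.1) missing subjects stay in that denominator as failures. Neither document gives another interval method or a rule for zero or very few responders.

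Table D-1, headed "External Placebo Data for Secondary Endpoints at Week 8", gives the external counts and a Beta prior for each secondary endpoint.

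**The concern.** The usual normal-approximation (Wald) interval takes its width from the observed proportion. When few or no responders are seen, that estimated width is too small, and at zero it vanishes. The SAP's own external data make such counts foreseeable for clinical and endoscopic remission.

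The problem extends to 9.5. Mucosal healing (SAP 3.0) and the endpoint requiring stool frequency, rectal bleeding and endoscopic subscores all equal to 0 (SAP 3.3) both need an endoscopic subscore of 0. At the same visit neither can be more frequent than endoscopic remission.

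What is at stake is how a low count is reported. The interval would show false precision, nearly always in one direction: its upper limit falls below the true rate.

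**Working it through.** **Inputs**

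- n = 40 (SAP 2.4), varied from 36 to 44 because the figure is approximate.
- Endoscopic remission on placebo (Table D-1): (2 + 2 + 2 + 3)/(122 + 112 + 154 + 174) = 9/562 = 1.60%. The table prints 2%; the prior Beta(9.0, 547.8) has mean 9.0/556.8 = 1.62%.
- Clinical remission on placebo: (7 + 7)/(154 + 174) = 14/328 = 4.27%. The table prints 4%; the prior Beta(14.0, 312.4) has mean 14.0/326.4 = 4.29%.

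The pooled counts therefore reproduce the plan's stated rates. Using them as the true ABBV-668 rate is an assumption.

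**Intervals at n = 40**

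Wald: x/n ± 1.96 × √[(x/n)(1 − x/n)/n]. For x = 1: 0.025 ± 1.96 × √(0.025 × 0.975/40) = 0.025 ± 0.048.

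| Responders | Wald | Wilson | Clopper-Pearson |
|---|---|---|---|
| 0/40 | [0, 0] | [0, 8.8%] | [0, 8.8%] |
| 1/40 | [−2.3%, 7.3%] | [0.4%, 12.9%] | [0.1%, 13.2%] |
| 2/40 | [−1.8%, 11.8%] | [1.4%, 16.5%] | [0.6%, 16.9%] |
| 3/40 | [−0.7%, 15.7%] | [2.6%, 19.9%] | [1.6%, 20.4%] |
| 14/40 | [20.2%, 49.8%] | [22.1%, 50.5%] | [20.6%, 51.7%] |

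The chance of 0 to 3 responders is 99.6% at a true rate of 1.6% and 91.0% at 4.3%.

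**Exact coverage**

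Coverage(p) = Σ C(40, x) pˣ (1 − p)⁴⁰⁻ˣ over every x whose interval contains p.

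- At p = 9/562 the Wald interval contains p only for x = 1 to 4. P(X = 0) = (1 − 9/562)⁴⁰ = 52.4% and P(X ≥ 5) = 0.04%, so coverage is 47.5%.
- At p = 14/328 it contains p only for x = 1 to 6. P(X = 0) = 17.5% and P(X ≥ 7) = 0.14%, so coverage is 82.4%.

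In both cases nearly every miss is an upper limit below the truth.

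| True rate | Wald | Wilson | Jeffreys | Clopper-Pearson |
|---|---|---|---|---|
| 1.6% (9/562) | 47.5% | 97.4% | 97.4% | 99.6% |
| 4.3% (14/328) | 82.4% | 97.3% | 97.3% | 99.3% |

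**Sensitivity of Wald coverage**

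- n from 36 to 44: 44.0% to 50.8% at 1.6%, and 78.8% to 85.1% at 4.3%.
- Rounded table rates at n = 40: 55.3% at 2% and 80.4% at 4%.
- Assumed doubling of the placebo rate: 72.6% at 3.2% and 86.1% at 8.5%.
- Mean (minimum) over assumed ranges at n = 40: 71.5% (47.5%) for 1.6% to 5%; 88.6% (79.5%) for 5% to 10%; 91.8% (86.1%) for 10% to 20%; 93.8% (91.9%) for 30% to 50%.

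**Alternatives from 1.6% to 10%, mean (minimum) coverage**

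Wilson 95.8% (91.8%); Clopper-Pearson 98.4% (95.3%); Jeffreys 95.4% (88.6%, near 6%).

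**Where the problem does not reach**

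The two response endpoints have placebo rates of 86/328 = 26% and 115/328 = 35%, where Wald coverage is about 91% to 95%. The placebo rate for the primary endpoint is redacted. If the planned 30% increase in SAP 2.4 means percentage points, the assumed ABBV-668 rate exceeds 30%; from 30% to 50%, coverage is 92% to 95%.

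**The case against.** The strongest reply is that nothing important rests on this interval. The secondary estimand is a difference from historical placebo. Table D-1 supplies a prior for every secondary endpoint, so the Bayesian comparison with its 95% credible interval can be run. It does not collapse at 0/40: by simulation the difference runs from about −2.5 to +4.5 points for endoscopic remission and from −6.2 to +2.1 points for clinical remission. The trial is a Phase 2a proof of concept without type I error control, and its only stated success measure is a posterior probability. The 48% and 82% also assume a drug no better than placebo; at a true rate of 10% or 15%, coverage is 91.4% or 93.9%.

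Much of this stands. It limits the point to descriptive reporting and means that the secondary endpoints would have a second measure of uncertainty. It does not remove the defect. A report with no responders would print [0, 0] beside a posterior that shows real uncertainty. A null or weak result is one that a proof-of-concept study must be able to report properly. Coverage is also not monotone: it is 83.7% at 8% and 86.8% at 12%, so a moderate benefit does not restore it reliably. For the additional endpoints in 9.5 no credible interval is stated at all.

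It is also fair to say that 9.3.2 gains little from a change, since at 14/40 the Wald and Wilson intervals nearly agree. The reason to change it is consistency.

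**Conclusion.** The concern holds. As written, SAP 9.4.2 and 9.5 produce intervals labelled 95% that are far from it at rates the SAP's own external data make plausible: 47.5% coverage for endoscopic remission and 82.4% for clinical remission at n = 40. At 0/40 the interval has zero width.

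These figures assume binomial counts, about 40 subjects in the denominator, and a true ABBV-668 rate equal to the pooled placebo rate; the shortfall is smaller if the drug raises these rates. The additional endpoints that require an endoscopic subscore of 0 are bounded by endoscopic remission at the same visit, but the documents give no rates for them. The primary inference and the Bayesian comparisons are unaffected. This should be corrected, but it does not threaten the trial's main conclusion.

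**What to change.** In SAP 9.4.2 and 9.5, and in 9.3.2 for consistency, replace the normal approximation with a named method: Wilson score or Clopper-Pearson exact. A Jeffreys interval from the Beta(0.5, 0.5) prior already in the plan would also be acceptable, although its coverage dips to about 89% near 6%. State how the interval is pooled across imputations if NRI-MI is run, because the responder count then varies between imputed data sets.

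The cost is three wording changes, the matching table programs and one sentence on pooling. Each alternative has a drawback: Clopper-Pearson is conservative (mean coverage about 98% from 1.6% to 10%), so somewhat wider than needed, and Wilson dips to about 92% at some low rates. The design, sample size, endpoints and primary analysis do not change.

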9.4.3 Sensitivity and Supplementary Analyses for Secondary Efficacy Endpoints

Similar analysis will be performed based on AO data.

9.5 Additional Efficacy Endpoints and Analyses

Additional efficacy endpoints described in Section 3.3 will be summarized at scheduled timepoints.

For additional binary endpoints, point estimate and 95% CI using normal approximation will be provided for the response rate of the ABBV-668 group. For additional continuous endpoints, the LS-mean and 95% CI will be reported for the ABBV-668 group using MMRM model, which includes visit, Baseline corticosteroid use (yes vs. no), Baseline

Mayo endoscopic sub-score (2 vs 3), TIM (including biologic and non-biologic) failure (Yes vs No) and Baseline measurement, if applicable. For endpoints with a single post-baseline visit, analysis of covariance (ANCOVA) will be used. Same covariates except for visit will be used. Similar analysis using RTB-MI may be performed as sensitivity analysis.

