5 STUDY ACTIVITIES

5.1 Eligibility Criteria

Subjects must meet all of the following criteria to be included in the study. Anything other than a positive response to the questions below will result in exclusion from study participation.

Consent

- 1. Subject must voluntarily **sign and date an informed consent**, approved by an independent ethics committee (IEC)/institutional review board (IRB), prior to the initiation of any screening or study-specific procedures.

Demographic and Laboratory Assessments

- 2. Adult **male or female**, at least 18 years old at time of the baseline visit.
- 3. **Laboratory values** meeting the following criteria within the screening period prior to the first dose of study drug:
 - Hemoglobin \geq 8 g/dL;
 - Serum aspartate transaminase (AST) and alanine transaminase (ALT) $\leq 2 \times$ upper limit of normal (ULN).
- 4. Are willing and able to comply with procedures required in this protocol.

- ✓ 5. Estimated glomerular filtration rate (eGFR) calculated by Cockcroft-Gault ≥ 90 mL/min at the Screening visit.

Disease/Condition Activity

- ✓ 6. Diagnosis of UC for at least 90 days prior to Baseline. Appropriate documentation of biopsy results consistent with the diagnosis of UC in the assessment of the investigator, must be available prior to enrollment.
- ✓ 7. Subject meets the following disease activity criteria: Active UC with an Adapted Mayo score of 5 to 9 points and ESS of 2 to 3 (confirmed by central review prior to enrollment).

Subject History

- ✓ 8. Subject must not have an active, chronic, or recurrent infection that based on the investigator's clinical assessment makes the subject an unsuitable candidate for the study, or the following:
 - Subject must not currently be positive with *C. difficile* toxin as identified during Screening or another known intestinal pathogen;
 - Subject must not be infected with human immunodeficiency virus (HIV);
 - Subject must not have active hepatitis B or hepatitis C (as defined in the Operations Manual);
 - Subject must not have evidence of active tuberculosis (TB) or meet TB exclusionary parameters (See specific requirements for TB testing in Section 3.13 of the Operations Manual).

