2.3 Treatment Assignment and Blinding

This is a single-arm, open-label study.

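### The one-arm LS-mean 95% CI for change from Baseline leaves out sampling error in the Baseline mean, so it is generally too narrow for the population mean change; by how much depends on a correlation and SD ratio the documents do not give.

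*SAP*

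**What the plan says.** SAP 9.5 covers the continuous additional endpoints: "For additional continuous endpoints, the LS-mean and 95% CI will be reported for the ABBV-668 group using MMRM model". SAP 9.2.2 gives the model. Its fixed effects are visit, Baseline corticosteroid use, Baseline endoscopic subscore, prior failure of targeted immunomodulator therapy, and "the continuous fixed covariate of Baseline measurement, if applicable". Estimation is by REML, and "An unstructured variance covariance matrix will be used", with simpler structures as a fallback. SAP 9.5 adds: "For endpoints with a single post-baseline visit, analysis of covariance (ANCOVA) will be used", with the same covariates apart from visit.

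The outcomes in SAP 3.3 are changes from Baseline, for example "Change from Baseline in SFS over time", and likewise rectal bleeding subscore (RBS), fecal calprotectin, hs-CRP, IBDQ and FACIT-Fatigue. SAP 2.3 says: "This is a single-arm, open-label study". SAP 2.4 says: "The planned sample size is approximately 40 subjects".

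The SAP does not say whether the interval is meant for the population mean change or is conditional on the Baseline values observed. It does not state how LS-means weight the categorical factors. It gives no SD or Baseline-to-visit correlation for any continuous endpoint.

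**The concern.** An LS-mean is a prediction at a chosen covariate value, normally the sample mean of Baseline. Its model-based standard error carries the residual variance given Baseline, but no allowance for the fact that another sample of 40 would have a different Baseline mean. In a randomised comparison both arms are predicted at the same Baseline value, so the omission cancels from the difference. Here there is no second arm and it stays in.

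The SAP plans no historical comparison for the continuous endpoints, so this interval is the main statement of uncertainty for them. A reader will take an unqualified 95% CI for mean change as an interval for patients of this kind. On that reading the precision is overstated.

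**Working it through.** **Inputs from the documents.** One arm (SAP 2.3); n=40 (SAP 2.4); Baseline as a fixed covariate (SAP 9.2.2); nominal level 95% (SAP 9.5). The documents state no coverage, SD or correlation for these endpoints, so there is no plan figure to reproduce.

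**Assumed inputs.** ρ is the correlation between the Baseline and visit values; 0.3, 0.5 and 0.7 are used. k is visit SD divided by Baseline SD; 0.7, 1 and 1.5 are used, with 0.5 as an extreme.

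**Formula.** Set the Baseline SD to 1. Regressing change on Baseline gives:

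- slope b = ρk − 1
- residual variance R = k²(1 − ρ²)
- total variance of change T = 1 + k² − 2ρk, which equals R + b²

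The model-based squared SE is R/n. With complete data and the LS-mean at the observed margins, the estimate is the raw mean change, whose variance about the population value is T/n = R/n + b²·Var(Baseline)/n. The SE ratio is √(R/T), which is √((1+ρ)/2) when k=1. Approximate coverage is 2Φ(1.96 × ratio) − 1. The widening needed is 1/ratio − 1.

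Example, k=1 and ρ=0.5: R = 0.75, T = 1.00, ratio = 0.866, coverage = 91.0%, widening = 15.5%.

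| k | ρ | R | T | SE ratio | Coverage | Widening |
|---|---|---|---|---|---|---|
| 0.7 | 0.3 | 0.446 | 1.07 | 0.646 | 79.4% | 54.9% |
| 0.7 | 0.5 | 0.368 | 0.79 | 0.682 | 81.9% | 46.6% |
| 0.7 | 0.7 | 0.250 | 0.51 | 0.700 | 83.0% | 42.9% |
| 1 | 0.3 | 0.910 | 1.40 | 0.806 | 88.6% | 24.0% |
| 1 | 0.5 | 0.750 | 1.00 | 0.866 | 91.0% | 15.5% |
| 1 | 0.7 | 0.510 | 0.60 | 0.922 | 92.9% | 8.5% |
| 1.5 | 0.3 | 2.048 | 2.35 | 0.933 | 93.3% | 7.1% |
| 1.5 | 0.5 | 1.688 | 1.75 | 0.982 | 94.6% | 1.8% |
| 1.5 | 0.7 | 1.148 | 1.15 | 0.999 | 95.0% | 0.1% |

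At k=0.5 the same formula gives about 66–67% for these correlations.

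**Simulation checks.** All used normal, complete data and n=40. Results are for ρ = 0.3 / 0.5 / 0.7.

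- *Baseline as the only covariate, 40,000 runs.* k=1: 89.0 / 91.3 / 93.2%. k=0.7: 80.3 / 82.4 / 83.4%. k=1.5: 93.2 / 94.5 / 95.0%. The paired t interval covered about 95% throughout.
- *ANCOVA with the three SAP factors, equal-weight LS-means, assumed factor prevalences, no factor effects.* k=1: 89.8 / 91.4 / 93.1% in one run and 90.0 / 91.6 / 93.8% in another. k=0.7, over several assumed prevalences: 82–86 / 84–87 / 86–88%.
- *Two-visit REML MMRM with unstructured covariance, 1,000 runs, k=1.* 87.8 / 90.1 / 92.1%.

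Adding b²·s_B²/n to the squared SE, where s_B is the sample Baseline SD, restored coverage to 95.0–96.0% in ANCOVA and about 93.6–95.5% in MMRM (Monte Carlo error about 0.7 points). Coverage conditional on the sample Baseline mean was 95% without any correction.

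**The case against.** **The size rests on inputs the documents do not give.** This stands. A reader might infer that the plan's intervals cover 89–93%, or never less than 80%. Neither follows without stating ρ and k. Coverage falls below 80% if the SD shrinks enough on treatment, and is close to nominal if it grows. Protocol 5.1 requires "Active UC with an Adapted Mayo score of 5 to 9 points and ESS of 2 to 3". This narrows the Baseline range of the stool frequency subscore (SFS) and RBS, so a larger SD at later visits is plausible for those two endpoints.

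**The interval is correct for a conditional target.** True, but the SAP does not declare one. Its estimand tables cover only the primary and secondary endpoints, and there the population is adults with moderately to severely active UC, not these subjects' Baseline mean.

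**Baseline enters only where applicable.** Where it is left out, the problem disappears. Every change-from-Baseline endpoint has a Baseline value, however, so the phrase gives no clear exemption.

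**The real model is richer than the formula.** This partly stands. With equal-weight LS-means the factors enlarge the SE and offset a few points of the shortfall, but do not remove it. With incomplete data the LS-mean is no longer the raw mean change. No skewed case was run, which matters for fecal calprotectin and hs-CRP.

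**Nothing is tested.** This stands. A reader might infer an inflated false-positive rate. The plan attaches no test or decision rule to these endpoints, so the fault is overstated precision in descriptive intervals.

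**Modelling Baseline as a repeated outcome is not a clean repair.** This also stands. For SFS and RBS, with eight post-Baseline visits, it raises the unstructured covariance from 36 (8×9/2) to 45 (9×10/2) parameters with about 40 subjects. Factor main effects would also cancel from the visit-minus-Baseline contrast unless interacted with visit.

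**Conclusion.** The point holds in mechanism and direction. As an interval for the population mean change, the planned one-arm LS-mean CI omits b²·Var(Baseline)/n and is too narrow unless b is near zero.

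Its size is conditional. At n=40 and assumed correlations of 0.3 to 0.7, coverage is about 89–94% with equal SDs (slightly lower in the two-visit MMRM). It is about 80–85% if visit SD is 0.7 times Baseline SD, a few points higher under some equal-weight settings and lower if the SD shrinks further. It is about 93–95% if visit SD is 1.5 times Baseline SD.

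The consequence is limited to the additional continuous endpoints. A reader might extend the criticism to the trial's main conclusions. The documents do not support that, because the primary and secondary endpoints are binary and are analysed without this model. The SAP should be corrected, but the point does not threaten the study's main result.

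**What to change.** In SAP 9.2.2 and 9.5:

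1. Keep the planned MMRM and ANCOVA.
2. State that the target is the population mean change, with LS-means at the observed covariate margins.
3. Obtain the 95% CI either by adding b²·s_B²/n to the squared model-based SE, or by bootstrapping subjects and refitting the whole model each time. The added term relies on the single Baseline slope in the SAP model. The bootstrap does not, and it also picks up sampling variation in the factor proportions.
4. Report the observed paired mean change with its t interval as a complete-case check. It should not replace the model, because it drops subjects with missing visits.

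The cost is SAP wording and some programming; no new data are needed. Intervals widen by about 8–24% with equal SDs and correlations of 0.3 to 0.7, by about 43–55% if visit SD is 0.7 times Baseline SD, and by 0.1–7% if it is 1.5 times. If the sponsor does want the conditional interval, the alternative is to say so in the SAP and in the table footnotes.
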